Statistical considerations	
Analysis populations: The Full Analysis Set (FAS) will be constituted by all the randomized patients. The Per-Protocol (PP) population will include all the patients of the FAS without major protocol violation during the course of the study.
 
All the efficacy analyses will be conducted on the FAS population and reproduced on the PP population for sensitivity purposes. The safety analyses will be conducted on the FAS, given that all randomized patients will receive at least one dose of treatment.
 
Primary efficacy analysis: The significance of the studied drug effect compared with Placebo will be tested by an Analysis of Covariance (ANCOVA) on the summary mean of ONLS at 12 and 15 months adjusted for baseline ONLS values. ANCOVA will be featured by a Linear Mixed Model (LMM), including baseline ONLS values and treatment as fixed factors, and center as random effect.
 
Two active doses will be compared to Placebo. As the monotonicity of dose effect is not assumed, each dose will be compared at a two-sided 2.5% significance level, in order to preserve an overall false-positive rate of 5%.
 
Sample size calculation: Assuming ANCOVA with 2 post-baseline measures, a linear correlation coefficient of ONLS of $R = 0.75$ between baseline and end of the study, a standard deviation of ONLS of $SD \cong 1$, a standardized mean difference of $SMD = 0.3$ should be detected versus Placebo with a power of 90% at a two-sided 2.5% significance level when the sample size reaches at least 89 patients per group. Assuming a drop-out rate of $\cong 10\%$, we anticipate recruiting 100 patients per group for a total of at least 300 patients.
 
Secondary efficacy analyses: The primary ANCOVA analysis based on the summary mean at 12 and 15 months will be repeated on the other quantitative efficacy endpoints (see above). The significance of the treatment effect on each quantitative endpoint will also be evaluated based on the difference compared to Placebo in change from baseline at each individual visit and in slope of progression over the duration of the study. The proportion of responders at 15 months will be assessed through a Generalized Linear Mixed Model (GLMM) featuring logistic regression, and admitting center as a random effect.
 
Missing data: Missing values will be imputed using a linear model estimated on the Placebo group. The potential impact of missing data on the study's conclusions will be evaluated.
 
Safety analyses: Safety and tolerability will be assessed by summarizing and analyzing adverse events (AEs), change in physical examination, vital signs, electrocardiogram (ECG) and laboratory data.
 
Data Safety Monitoring Board (DSMB): An independent DSMB will regularly follow the progress of the clinical trial, monitor safety data and critical efficacy variables, and be consulted concerning the opportunity of modifying the sample size or terminate the trial for futility.
 
Adaptive sample size: An estimation of the adjusted standard deviation (ASD) will be performed when 80 patients are available. In case where the absolute value of the difference between the observed ASD and the value used for initial sample size calculation

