2. STUDY DESIGN

From V1.4: the dose 2 arm is discontinued due to unexpected IMP quality event, the occurrence of crystals observed in the dose 2 IMP

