8.4.1.2 Secondary efficacy endpoints

In the context of an orphan disease, when there are no ideal endpoints, it might be acceptable to assess multiple endpoints and to observe their outcomes. However, they have been selected according to our experience from the previous phase 2 study, and they are hierarchized as following:

- Responders Rate to PXT3003 therapy defined as a patients improving on ONLS at end of treatment.
- Clinical and functional tests:
 - Arm and leg sub-items of ONLS,
 - Charcot-Marie-Tooth Neuropathy Score version 2 (CMTNS-V2), total score and sub-items,
 - Nine-Hole Peg Test (9-HPT) performed on the non-dominant hand,
 - Hand grip Quantified Muscular Testing (QMT) and foot dorsiflexion QMT performed on both sides,
 - Time to walk 10 meters,
- Exploratory efficacy endpoints:
 - Electrophysiological parameters assessing sensory and motor responses of ulnar and radial nerves (non-dominant side):
 - Compound Muscle Action Potential (CMAP) on ulnar nerve,
 - Sensory Nerve Action Potential (SNAP) on radial nerve,
 - Nerve conduction velocity (NCV),
 - Quality of life measured by:
 - EuroQol 5-Dimensional Health-related Quality of Life scale (EQ-5D),
 - VAS on self-assessment of the individualized main impairment in daily activities defined at baseline with the patient,

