8.4.1.3 Discussion on the choice of the efficacy endpoints

A. ONLS is a disability scale that was derived and improved from the Overall Disability Sum Score by (Graham and Hughes, 2006) to measure limitations in the everyday activities of the upper limbs (rated in 5 points) and the lower limbs (rated on 7 points) (See Appendix II). The total score goes from 0 (= no disability) to 12 (= maximum disability). Although the functioning of patients with peripheral neuropathy may be influenced by other factors in addition to their physical capacity, ONLS measures the perceived ability of the patient to move and fulfil normal life, and thus expected to be associated with Quality of Life. It was initially validated in a pool of 100 patients with diverse peripheral neuropathies (mainly of dysimmune origin but including 9 CMT patients, 11 patients with chronic idiopathic axonal polyneuropathy, and 13 patients with paraprotein-associated demyelinating neuropathy): it showed significant relationships with measures of impairment, disability and quality of life.

The 136th ENMC Workshop agreed in recommending the ONLS as the core disability scale for CMT1A trials (Reilly, de Jonghe *et al.*, 2006), and its reliability was subsequently further validated in 40 CMT patients (Solari, Laura *et al.*, 2008).

ONLS was shown to be more sensitive to change compared with CMTNS, as found in a recent analysis on the 34 CMT1A patients enrolled successively in two clinical trials. The first tested Acid Ascorbic (a phase II randomized placebo-controlled trial performed at three hospital sites from September 2005 to October 2008 on 180 patients (Micallef, Attarian *et al.*, 2009)), and the second was conducted 5 years later, testing PXT3003 (a Phase II placebo-controlled trial performed at six hospital sites from December 2010 to November 2012 on 80 patients (Attarian, Dubourg *et al.*, 2013)). During the five years between the two assessments, no modification on CMTNS, Charcot-Marie-Tooth Examination Score (CMTES) or motor and sensitive amplitudes were reported, while a significant increase of ONLS score was noticed. It is known that CMT1A is a progressive neurodegenerative disease and the natural progression of the disability during the 5 years between the two studies was shown by the ONLS while the CMTNS did not reflect the disease progression.

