14.2 Primary efficacy analysis

The significance of the studied drug effect compared with Placebo will be tested by an Analysis of Covariance (ANCOVA) on the summary mean of ONLS at 12 and 15 months adjusted for baseline ONLS values. ANCOVA will be featured by a Linear Mixed Model (LMM), including baseline ONLS values and treatment as fixed factors, and center as random effect. The use of two repeated post-baseline measures increases the power to detect treatment differences in mean levels of the outcome measure over time (Frison and Pocock, 1992; Morgan and Case, 2013).

Two active doses will be compared to Placebo. As the monotonicity of dose effect is not assumed, each dose will be compared at a two-sided 2.5% significance level, in order to preserve an overall false-positive rate of 5%.

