14.3 Sample size calculation

Assuming ANCOVA with 2 post-baseline measures, a linear correlation coefficient of ONLS of $R = 0.75$ between baseline and end of the study, a standard deviation of ONLS of $SD \approx 1$, and a negligible between center standard deviation (estimated $SD = 0.13$ [0;0.35]), the resulting adjusted standard deviation $ASD \approx [1*(1-.75^2)]^{.5} \approx 0.65$, thus a minimum clinically relevant difference in ONLS should be a Cohen's Δ of $0.65/2 \approx 0.325$, rounded to $\Delta = 0.3$. From calculations based on compound symmetry of the covariance matrix (Frison and Pocock, 1992, Morgan and Case, 2013), such a difference should be detected versus Placebo with a power of 90% at a two-sided 2.5% significance level when the sample size reaches at least 89 patients per group. Assuming a drop-out rate of $\approx 10\%$, we anticipate recruiting 100 patients per group for a total of at least 300 patients.

The parameters needed for sample size calculation were evaluated based on historical trials (Micallef, Attarian *et al.*, 2009; Pareyson, Reilly *et al.*, 2011; Attarian, Vallat *et al.*, 2014).

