14.4 Secondary efficacy analyses

The primary ANCOVA analysis based on the summary mean at 12 and 15 months will be repeated on the other quantitative efficacy endpoints (see above). The significance of the treatment effect on each quantitative endpoint will also be evaluated based on the difference compared to Placebo in change from baseline at each individual visit and in slope of progression over the duration of the study. The proportion of responders at 15 months will be assessed through a Generalized Linear Mixed Model (GLMM) featuring logistic regression, and admitting center as a random effect. Secondary analyses will be conducted at a two-sided 5% significance level.

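### The 15-month responder model names only center; naming treatment and baseline ONLS as well would complete it and avoid a modest loss of precision

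*Combined protocol and SAP*

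**What the plan says.** Section 8.4.1.2 puts the responder rate first among the secondary endpoints, with responders "defined as a patients improving on ONLS at end of treatment". It gives no numeric threshold.

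For the analysis, section 14.4 specifies a "Generalized Linear Mixed Model (GLMM) featuring logistic regression, and admitting center as a random effect", and center is the only model term named. The synopsis matches: "The proportion of responders at 15 months will be assessed through a Generalized Linear Mixed Model (GLMM) featuring logistic regression", again with center alone added. Section 14.4 sets the secondary tests at two-sided 5%.

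The primary model in section 14.2 is written out in full, "including baseline ONLS values and treatment as fixed factors, and center as random effect". Section 14.4 carries that ANCOVA over to further endpoints, but says only that it "will be repeated on the other quantitative efficacy endpoints". A binary responder outcome is not one of those. Section 14.9 and the synopsis leave further statistical detail to the SAP, and nothing in the combined document adds baseline ONLS to the responder model.

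**The concern.** A responder is defined by change from the starting score. With an imperfect correlation between baseline and 15 months, patients who start high are more likely to improve than patients who start low, through regression to the mean alone. Baseline ONLS is therefore a strong predictor of response, and the primary analysis already uses it. A logistic model without it stays valid but gives up precision on a value already collected at V1. As written, two analysts could also fit different models and both claim to follow section 14.4.

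**Working it through.** **Inputs.** From section 14.3: ONLS SD about 1, "a linear correlation coefficient of ONLS of $R = 0.75$ between baseline and end of the study", difference 0.3, 89 evaluable patients per group, between-center SD negligible. From section 14.4: two-sided 5%. From Appendix 2: ONLS is a whole-number score. Assumed, because the documents do not give them: baseline mean 2 to 4, equal variance at both times, a pure shift of 0.3. No center effect was modelled.

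**1. The plan's own figure.** With two post-baseline measures under compound symmetry, the ANCOVA variance is (1 + 0.75)/2 − 0.75² = 0.3125. Then n = 2 × (2.241 + 1.282)² × 0.3125 / 0.3² = 86.2, so 87 per group (88 with the noncentral t), against 89 stated. Power at 89 is 0.91, and 89/0.9 = 99, rounded to 100. The inputs reproduce the plan's figure. The documents state no power for the responder endpoint.

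**2. Does baseline predict response?** For the whole-number score at mean 3, the simulated placebo response is 5%, 10%, 20%, 34% and 50% at baseline scores 1, 2, 3, 4 and 5.

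**3. One case by hand** (unrounded score, fall of at least 0.5). The SD of change is √(2 × (1 − 0.75)) = 0.707. Response is 1 − Φ(0.5/0.707) = 0.240 on placebo and 1 − Φ(0.2/0.707) = 0.389 on active.
- Without baseline: log odds ratio 0.701, SE √(1/(89 × 0.240 × 0.760) + 1/(89 × 0.389 × 0.611)) = 0.330, z = 2.124, power Φ(2.124 − 1.960) = 56.5%.
- With baseline: log odds ratio 0.757, SE 0.344, z = 2.201, power 59.5%.
- Information loss: 1 − (2.124/2.201)² = 6.8%.

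**4. All cases at R 0.75, 89 per group, two-sided 5%.**

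| Score and cut-off | Response, placebo / active | Power without baseline | Power with baseline | Points lost | Information lost |
|---|---|---|---|---|---|
| Unrounded, any fall | 50.0% / 66.4% | 59.9% | 63.1% | 3.2 | 7.2% |
| Unrounded, fall ≥ 0.5 | 24.0% / 38.9% | 56.5% | 59.5% | 3.0 | 6.8% |
| Unrounded, fall ≥ 1.0 | 7.9% / 16.1% | 38.3% | 39.9% | 1.7 | 5.0% |
| Whole-number, R 0.75 on the observed score, mean 2 to 4 | about 22% / 38% | 63.4–64.2% | 67.9–68.1% | 3.9–4.6 | 8.0–9.2% |
| Latent score with R 0.75, then rounded, mean 3 to 4 | 25.7% / 39.7% | 50.7–50.8% | 55.0–55.1% | 4.3 | 10.0–10.1% |
| Same, mean 2 | 25.4% / 39.0% | 48.8% | 53.7% | 4.9 | 11.6% |

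The fourth row comes from 40,000 simulated trials per mean, and the others from the normal approximation. A further simulation put adjusted power in the fourth row at 68 to 70%. In information terms the loss equals 0.050 × 89 = 4.5 to 0.116 × 89 = 10.3 patients per group.

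**5. Sensitivity to R.**
- R 0.6: 11.7 to 12.0% for the unrounded score with cut-off 0 or 0.5 (9.8% at cut-off 1.0), 12.6 to 14.0% for the observed whole-number score, and 14.6% (5.2 points) for the rounded latent score at mean 3. At mean 2 the last becomes 1 − (1.605/1.752)² = 16%.
- R 0.9: 2.2 to 2.4% (0.6 to 0.8 points) unrounded with cut-off 0 or 0.5, 1.0% (0.3 points) at cut-off 1.0, 4.1 to 5.0% (under 1 point) for the observed whole-number score, and 5.6% (2.4 points) for the rounded latent score at mean 3.

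**6. Type I error.** With no drug effect and R 0.75, rejection is 4.80 to 4.93% without baseline and 4.85 to 4.87% with it.

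**The case against.** The strongest reply is that silence is not omission. The same sentence does not name treatment, and a model without treatment could not test the drug, so it must be shorthand. It follows directly on a sentence that repeats the baseline-adjusted ANCOVA, and detail is left to the SAP. This stands. A reader might infer that the plan excludes baseline ONLS; the documents do not support that, and every loss above is conditional on the model being run without it.

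Second, no single loss or power can be claimed. Baseline mean and expected responder rates are not given, and section 14.8 itself allows that SD and R may be wrong. This also stands, which is why ranges are shown.

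Third, an unadjusted comparison of responder proportions is a legitimate analysis, and adjustment changes what the odds ratio means. In the simulation of the observed whole-number score it moves from about 2.2 to about 2.4 for the same drug effect. This is a real but small cost, met by labelling the odds ratio and showing the observed proportions.

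Fourth, a reader might infer that the gain concerns dose 1 versus placebo only, because section 2 says "the dose 2 arm is discontinued due to unexpected IMP quality event". That is plausible, but it is an inference. No completer count is given, all randomized patients enter the efficacy analyses (section 14.1), and missing values are to be imputed (section 14.5).

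**Conclusion.** The point holds as a modest, conditional efficiency point on a secondary endpoint for which no power was planned. The responder model is under-specified. If it were fitted without baseline ONLS, about 5 to 12% of the information, or about 1 to 5 power points, would be lost at the plan's R of 0.75. Across R 0.6 to 0.9 the loss is about 2 to 15%, with extreme combinations at 1% and 16%, and at R 0.9 it can be under 1 power point. Absolute power at R 0.75 lies anywhere from about 38% to about 70%, depending on assumptions the documents do not fix.

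A reader might go further and see bias or a threat to the trial's main result. Neither follows: type I error is held with or without the covariate, and the primary analysis already adjusts for baseline.

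**What to change.** In section 14.4 and the synopsis, and in the SAP they refer to, specify the responder GLMM with treatment and baseline ONLS as fixed effects and center as a random effect. State that the resulting odds ratio is conditional on baseline ONLS and center, and report the observed responder proportion in each arm beside it. Fix this before unblinding so that the covariate is not a later choice.

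The cost is wording only. ONLS is already measured at V1 (flow chart and section 11.2.2), so no data, visits or procedures are added.

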In parallel, the FDA expressed concern about CMTNS. While it is commonly used to assess disease severity, CMTNS may not be appropriate to evaluate the potential clinical benefit of a drug given that it is a composite score based on patient signs, symptoms and neurophysiological measures, with potentially different meanings and interpretation. The FDA advised to select a primary endpoint more directly related with drug benefit: in particular ONLS might be more appropriate as a specific disability estimate with functional scale grades for legs and arms.

The other usual endpoints will be used as secondary endpoints and they will be hierarchized as clinical, functional, electrophysiological and other exploratory endpoints. Secondary endpoints should be ordered in a hierarchical manner with statistical adjustment for multiplicity.

Out of these points, both agencies endorsed the proposed study population, the choice of doses and the key points of the design.

Therefore, if this single pivotal phase III study provides positive confirmatory results, it should be sufficient to support the marketing application of PXT3003 in the treatment of CMT1A adult patients.

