The walking tests are expected to be partly correlated with ONLS, CMTNS and QMT. However, in the previous clinical trials, 6-Minutes Walking Test (6-MWT) was used, but a clear training effect was shown along the successive visits in all groups, with no difference with the placebo group so that finally it does not seem to be relevant to evaluate CMT disease. The 6-MWT is time consuming and requires a large space to be practiced.

Better than an endurance test on a long distance, most of the interviewed experts prefer to test the speed to walk on a small distance as the limited dorsiflexion in CMT induces walk impairment particularly at start. The time to walk 10 meters is proposed.

The 10m WT is simple to administer, standardized, reliable and valid evaluation of functional exercise capacity and gait that has been proven reliable in neurologic disorders (Watson, 2002; Tyson and Connell, 2009) and in CMT patients (Solari, Laura *et al.*, 2008). Results recorded are the time to walk 10 meters and the number of steps performed.

Even if walk tests have been proven reliable in other pathologies including neurologic disorders, their reliability and sensitivity are not established in CMT and need to be assessed. The walking test is sensitive to fatigue related changes and to ankle status (walk ability may be modified if orthese or surgery) and it correlates with established outcome measures. However it only reflects the ability to walk 10 metres in a controlled environment at a constant speed. The walking test is expected to be partly correlated with ONLS, CMTNS and QMT.

F. Electrophysiological parameters

Sensory and motor responses measured at ulnar and radial nerves on the non-dominant side:

- Compound Muscle Action Potential (CMAP) on ulnar nerve
- Sensory Nerve Action Potential (SNAP) on radial nerve
- Nerve Conduction Velocity (NCV)

For CMT, it is usual to measure motor and sensory amplitudes of one nerve (ulnar is recommended for CMAP and radial for SNAP in the modified CMTNS version 2).

CMAP appears as weakly reliable since affected by the positioning of the electrodes and hence is physician-dependent. NCV is a more reliable measure since relatively unaffected by the electrodes positioning and is only affected by the skin temperature.

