14.9 Futility analysis

A one-stage Futility stopping will be based on Conditional Power, probability to detect a significant result at the end of the study, given the results observed at an intermediate time. Conditional Power (CP) will be estimated through B-values and (Lan and Wittes, 1988; Lan and Zucker, 1993). This analysis will be carried out by a third party statistician when at least 100 patients are available, and futility threshold will be $CP_{min} = 0.10$ involving a slight increase of type 2 error ($\beta = 0.1/0.9 = 0.111-0.10 \cong 0.01$) (Proschan, 1999). This intermediate futility analysis does not require any type-I adjustment, this trial does not plan g rejection of the null hypothesis before its end.

Further details will be described in the Statistical Analysis Plan (SAP) as appropriate.

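### Section 14.4 tests every secondary endpoint at two-sided 5% with no testing order, gate on the primary, adjustment or dose split, although section 7 calls for ordering and adjustment

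*Combined protocol and SAP*

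**What the plan says.** - Section 14.4 repeats the primary ANCOVA on the other quantitative endpoints. It adds significance tests against placebo "in change from baseline at each individual visit and in slope of progression over the duration of the study", and tests the month-15 responder proportion with a logistic mixed model. It closes with: "Secondary analyses will be conducted at a two-sided 5% significance level". The synopsis lists the same analyses and has no multiplicity rule for them.
- Section 7, in its account of the endpoint discussions with the agencies: "Secondary endpoints should be ordered in a hierarchical manner with statistical adjustment for multiplicity".
- Section 8.4.1.2 introduces the secondary endpoints with "they are hierarchized as following". Responder rate comes first, then the clinical and functional tests, then endpoints labelled exploratory.
- Section 14.2, for the primary: "each dose will be compared at a two-sided 2.5% significance level, in order to preserve an overall false-positive rate of 5" percent.
- Section 14.9 ends with a general pointer: "Further details will be described in the Statistical Analysis Plan (SAP) as appropriate". The supplied text contains no testing order.

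**The concern.** The protocol controls multiplicity across doses for the primary endpoint and says in section 7 that the secondaries need ordering and adjustment. The section that governs the secondary tests then does neither. Read as written, every secondary test on either dose that reaches p < 0.05 is significant, whatever happened on ONLS.

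The list in 8.4.1.2 does not close the gap as it stands. ONLS arm and leg share one bullet, CMTNS-v2 total and its sub-items share another, and grip and foot dorsiflexion share a third. The two doses, the individual visits and the slopes have no place in it.

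Section 7 presents this as a single pivotal trial meant to support a marketing application. A dose that fails on ONLS could still be reported with significant secondary results at an uncontrolled error rate, and the order of importance could be settled after the results are known.

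**Working it through.** **1. The plan's own figure.** Primary alpha: 0.025 + 0.025 = 0.05, as section 14.2 states. Because both doses share the placebo arm (correlation 0.5 between the two test statistics), the actual rate under the null is 0.0465. The plan states no familywise figure for the secondaries.

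**2. Counting the tests.**
- Non-exploratory endpoints in 8.4.1.2: responder rate, ONLS arm, ONLS leg, CMTNS-v2 total, 9-HPT, grip, foot dorsiflexion, 10 m walk = 8. CMTNS-v2 sub-items are not counted.
- Labelled exploratory: CMAP, SNAP, NCV, EQ-5D, VAS = 5, giving 13 in all.
- Analyses per quantitative endpoint in 14.4: the 12/15-month mean, three visits (6, 12 and 15 months) and slope = 5. For the 8 endpoints this is 7 × 5 + 1 = 36 tests per dose, 72 for two doses. At 5% each, 72 × 0.05 = 3.6 false positives are expected if every null hypothesis is true.

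**3. If all tests were independent,** one analysis per endpoint at 5%:
- One dose, 8 endpoints: 1 − 0.95^8 = 0.34.
- Two doses, 16 tests: 1 − 0.95^16 = 0.56.
- Two doses, 13 endpoints, 26 tests: 1 − 0.95^26 = 0.74.

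**4. With a shared placebo and correlated endpoints.** The documents give no correlations between endpoints, so 0 to 0.7 is an assumed range. The table comes from 400,000 simulated null trials per setting, with three equal arms, equal correlation r between all endpoints (primary included), and one analysis per endpoint. It shows the chance of at least one false secondary result.

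| Rule | r = 0 | 0.3 | 0.5 | 0.7 |
|---|---|---|---|---|
| 8 endpoints, two doses, 5% per dose | 53% | 48% | 41% | 32% |
| Same, among trials where neither primary test is significant | 53% | 48% | 40% | 30% |
| 8 endpoints, two doses, 2.5% per dose | 32% | 29% | 24% | 19% |
| 8 endpoints, one dose at 5% | 34% | 30% | 25% | 19% |
| 13 endpoints, two doses, 5% per dose | 71% | 63% | 53% | 40% |

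The right-hand columns are probably nearer the truth. Responder status and the arm and leg items derive from ONLS, and section 8.4.1.3 says "The walking test is expected to be partly correlated with ONLS, CMTNS and QMT".

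**5. If visit and slope tests also count as claims** (36 tests per dose, visit-to-visit correlation set to the 0.75 of section 14.3): 67–88% at 5% per dose, 45–67% at 2.5% per dose, and 45–68% for one dose at 5%. The plan does not define the slope model. At 5% per dose, an ordinary least-squares slope gives 68–89% and a slope through the origin 65–86%.

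**6. After the fix.** With a fixed sequence per dose at 2.5%, run only after that dose's primary succeeds, a false secondary result under the null needs a false primary result first. Simulated: 0.1% at r = 0 rising to 1.3% at r = 0.7 for any false secondary result, and 4.6–4.7% for any false primary or secondary result. If a primary effect is real and the secondaries are null, each dose still contributes at most 0.025, so the total stays at or below 0.05. Halving alpha by dose without an order does not achieve this (19–32% above). A plain Bonferroni correction over 16 tests would need 0.05 / 16 = 0.0031 per test.

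**The case against.** - **A hierarchy exists in the text.** Section 8.4.1.2 calls its list hierarchized, and section 7 ranks the classes of endpoint. This stands as an order of importance. It is not a testing order: 14.4 does not use it as one, and several bullets hold more than one test.
- **Section 7 and 14.4 are not strictly incompatible.** A fixed sequence at full alpha could carry a 5% level, and section 7's sentence says should and may be reporting agency advice. The first part is right: the fault is an omission from 14.4, not a flat contradiction. Even as advice, it is unanswered in the operative section.
- **The secondaries are only supportive.** Section 8.4.1.2 suggests that in an orphan disease several endpoints may be assessed and their outcomes observed. That sentence sets no error rule, whereas 14.4 sets a significance level. If support is all that is meant, 14.4 should call the p-values nominal.
- **The SAP may settle it.** A separate SAP could hold a testing order, but the supplied text does not show one. The fix allows for this.
- **The error rates rest on assumptions.** They assume no effect on any endpoint, and correlations the documents do not give. This is true, and is why a range is shown. At r = 0.7 the two-dose rate is still 32%. The visit and slope figures depend most on assumption, and the conclusion does not need them. The 0.1% lower bound after the fix requires responder status to be independent of ONLS; about 1.3% is more realistic.
- **Dose 2 was stopped.** Section 2 says "the dose 2 arm is discontinued due to unexpected IMP quality event", but the amendment sends its incomplete data to section 14.5 and does not remove the comparison. With one dose only, 19–34% remains.

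**Conclusion.** The concern holds. Section 14.4 leaves the secondary tests without an order, a gate, an adjustment or a dose split, and section 7 calls for both ordering and adjustment. With no true effect, two doses, 8 endpoints analysed once each and 5% per dose, the chance of at least one false secondary result is 32–53% over the assumed correlations; for one dose it is 19–34%. The primary test, its alpha and the sample size are untouched. This should be fixed before unblinding. Confidence is high about what 14.4 says; whether a separate SAP supplies the missing rule cannot be seen from the supplied text.

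**What to change.** Replace the last sentence of section 14.4 with:

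> For each dose, and only if that dose's primary ONLS test is significant at its two-sided 2.5% level, secondary endpoints are tested at that same level, stopping at the first non-significant result, in this order: (1) responder rate at month 15; then, on the 12/15-month summary mean, (2) ONLS arm, (3) ONLS leg, (4) CMTNS-v2 total, (5) 9-HPT, non-dominant hand, (6) hand grip, mean of both sides, (7) foot dorsiflexion, mean of both sides, (8) time to walk 10 m. CMTNS-v2 sub-items, electrophysiology, quality-of-life, per-visit and slope comparisons are descriptive, with nominal p-values.

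This follows the text order of 8.4.1.2 and the per-dose level of 14.2. The order is a choice: putting the responder rate first means that a miss there ends formal testing for that dose. The team may fix another order before unblinding, provided it is complete. The synopsis should match. If the SAP already sets an order, 14.4 should refer to it.

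The cost is protocol and SAP wording only, with no new data or patients. The downside is that fewer secondary results can be called significant, and an early miss stops formal testing of later endpoints for that dose.
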